11.2 Secondary study parameter(s)

The differences in NRS-scores pre- and postoperative of anxiety in both groups (VR-intervention and standard-care group) will be analyzed using the linear mixed models analysis. The results of the STAI-questionnaire, PCS questionnaire, analgesic use and length of hospital stay will be calculated into means with standard deviation and confidence interval. We want to compare the baseline characteristics and questionnaires (STAI and PCS) to see whether the groups are equally divided. The STAI and PCS questionnaire are continuous variables, we will use the independent sample t-test. The tolerability, feasibility and satisfaction of VR use will be calculated into means and frequencies.

11.3 Other study parameters

Not applicable

11.4 Interim analysis

Not applicable

12. ETHICAL CONSIDERATIONS**12.1 Regulation statement**

The study will be conducted according to the principles of the Declaration of Helsinki (version 64, WMA General Assembly, Fortaleza, Brazil, October 2013)) and in accordance with the Medical Research Involving Human Subjects Act (WMO).

12.2 Recruitment and consent

Women who were planned for elective gynecological surgery under spinal anesthesia will be informed about the study during their visit at the outpatient clinic. Eligible patients who fulfill the inclusion criteria will be identified and counselled by the research coordinator or staff of the Zuyderland Medical Centre. Before entry into the study, the research coordinator and/or the staff will explain to potential participants the aims, methods, reasonably anticipated benefits, and potential hazards of the study. They will be informed that their participation is voluntary and that they may withdraw consent to participate at any time during the study. They will be informed that choosing not to participate will not affect their care. After giving sufficient information, written informed consent must be obtained

12.3 Objection by minors or incapacitated subjects (if applicable)

Not applicable.

12.4 Benefits and risks assessment, group relatedness

The risks of this research will be small, according to the CTCM. Possible rare side-effects of the use of VR can be: nausea, dizziness and vomiting. Whenever a patient experiences side-effects or hindrance of the study, she can decide to withdraw. Benefits of the study: probably less pain after gynecological surgery with spinal anesthesia and less anxiety in the pre- and postoperative setting.

Previous studies reported transient adverse events such as nausea and dizziness, but no major adverse events [20-24]. The risks of VR therapy for the participants are negligible. Previous studies described significant reductions of acute pain scores after a single VR session.

12.5 Compensation for injury

The sponsor/investigator has a liability insurance which is in accordance with article 7 of the WMO. The sponsor (also) has an insurance which is in accordance with the legal requirements in the Netherlands (Article 7 WMO). This insurance provides cover for damage to research subjects through injury or death caused by the study.

The insurance applies to the damage that becomes apparent during the study or within 4 years after the end of the study.

12.6 Incentives

Not applicable.

13. ADMINISTRATIVE ASPECTS, MONITORING AND PUBLICATION

13.1 Handling and storage of data and documents

An encrypted Excel keyfile will be made. In this file, the patient numbers will be linked to the concerning study number. Only the (head)investigators will have access to this file. The obtained data will be saved as eCRF in the program 'Research Manager'. Also, here only the (head) investigators have access. The data will be saved for 15 years, according to the regular agreements. As well as for the Excel keyfile as for the Research Manager a password is necessary. All paper documents (informed consent and questionnaires) will be stored in one folder. This folder will be saved in a locked closet in the room of the head investigator. On the informed consent form no study number will be mentioned, so that a study number cannot be traced back on paper to a patient. The data will be collected in a digital data management system (research manager).

When data of a patient must be derived from the electronic patient files, then this will be done by investigator [name]. In principle, all the information can be given by the patient, and the patient file does not have to be seen.

When the patient participates in the study, this will be noted in the patients document of the hospital. The study number will be determined at the day of surgery. The inclusion will be done by one of the doctors of the Gynecology department of the Zuyderland Medical Centre. They will be instructed how to include the patients and which patients are suitable to be included in the study. Data of the study will not be shared with persons and/or organizations other than the Zuyderland Medical Centre.

13.2 Monitoring and Quality Assurance

According to the local guidelines of 'Bureau Wetenschappelijk Onderzoek (BWO)' the study will be monitored by Clinical Trial Centre Maastricht (CTCM). The CTCM classified the study as 'negligible/low risk'. They are producing the monitoring plan. When the monitoring plan is finished, it will be uploaded on Research Manager.

In our opinion, this study adds a rare small chance of reversible mild damage and consequently adds a negligible risk according to the risk classification of the "Nederlandse Federatie van Universitaire Medische Centra" (NFU). Monitoring will be conducted in accordance with negligible risk monitoring guidelines of the NFU, which will be reported in a monitoring plan.

13.3 Amendments

Amendments are changes made to the research after a favorable opinion by the accredited METC has been given. All amendments will be notified to the METC that gave a favorable opinion.

13.4 Annual progress report

The investigator will submit a summary of the progress of the trial to the accredited METC once a year. Information will be provided on the date of inclusion of the first subject, numbers of subjects included and numbers of subjects that have completed the trial, serious adverse events/ serious adverse reactions, other problems, and amendments.

13.5 Temporary halt and (prematurely) end of study report

The investigator will notify the accredited METC of the end of the study within a period of 8 weeks. The end of

the study is defined as the last patient's last visit.

Within one year after the end of the study, the investigator will submit a final study report with the results of the study, including any publications/abstracts of the study, to the accredited METC.

13.6 Public disclosure and publication policy

Not applicable

14. STRUCTURED RISK ANALYSIS

Not applicable

14.1 Potential issues of concern

The potential risk of the study is negligible. Virtual Reality in the medical world has been used for a couple of years nowadays. The chance of interaction with medication or other products is zero. Participants of the study will get an explanation of VR before using the product.

14.2 Synthesis

Not applicable.

Performance: the patients gets a clean hairnet and the VR-glasses with fake leather cover on the head. By using the net, the headbands of the glasses will stay clean. After use of the VR-glasses, it needs to be cleaned using the Incidin Oxyfoam (or comparable alcoholic disinfection). After use the hairnet can be thrown away. The VR glasses are ready to be used by the next patient.

Attachment 2. Baseline characteristics

Age, BMI, ethnicity, education level, marital status, vaginal parity, ASA-classification, medication use, intoxications, chronic pain, surgical history, indication of surgery

1. Age

..... years

2. Length

..... cm

3. Weight

.....kg

4. Etnicity (when you rather not fulfill this question, you can fil in 'unknown')

- Kaukasian
- Latin-American
- Azian
- African
- Turkish
- Other ethnicity
- Unknown

5. Education (when you rather not fulfill this question, you can fil in 'unknown')

- Primary school
- High school
- Community college
- University
- Unknown

6. Marital status (when you rather not fulfill this question, you can fil in 'unknown')

- Single
- Living together
- Married
- Unknown

7. Smoking

- Yes,..... sigars/sigarrettes per day/week/month
- No

8. Alcohol

- Yes,..... glasses per day/week/month
- No

9. Drugs

- Yes,..... per day/week/month
- No

10. Vaginal delivery's

- 0
- 1
- 2
- 3
- 4
- >5

11. Medication use

.....

12. When using medication, do you use morphine? (e.g. oxycodon, oxycontin, morphine, fentanyl or others?)

.....

13. Do you have chronic pain (existing for more than 6 months) not related to the reason of the surgery?

- Yes
- No

14. Have you ever had surgery before?

- Yes
- No

15. When you answered 'yes' on question 14, what kind of surgery did you have?

.....

16. ASA classification (will be filled in by your doctor)

- ASA 1
- ASA 2
- ASA 3
- ASA 4

17. Indication of surgery (will be filled in by your doctor)

.....

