5.3 Exclusion criteria

- Chronic pain patients; defined as 'persistent or recurrent pain lasting longer than 3 months' [16]. The pain is not due to the gynecological problem.
- Chronical use of pain medication (opioids)
- History of prior opioid use defined as use within 8 to 90 days prior to the surgical procedure
- Alcohol or drug abuse
- Known car sickness
- Epileptic insults in previous history
- Psychotically seizures in previous history
- Claustrophobic
- Blindness
- History of mental illness

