9.1.3 Other study parameters

The following baseline characteristics will be collected pre-operatively; age, BMI, ethnicity, education level, marital status, vaginal parity, ASA-classification, medication use, intoxications, chronic pain, surgical history, indication of surgery, type of planned surgery. When patients do not want to answer certain questions, for example marital status or education level, they are free to answer 'unknown'. It is possible that these characteristics may be of influence of pain experience or the experiences in VR. These can be confounders in the study.

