11.1 Primary study parameter(s)

The differences in postoperative NRS-scores of pain in between both groups (VR-intervention and standard-care group) will be analyzed using the linear mixed models analysis. The NRS-score of pain of the VR group and standard-care group will be compared to see whether VR influences the pain experience. Different variables, like age, BMI, ethnicity, education level, marital status, vaginal parity, ASA-classification, medication use, intoxications, chronic pain, surgical history, indication of surgery, type of planned surgery, will be considered in the statistical analysis. These are taken into account because these variables can be possible confounders in the results of the study.

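### The only chronic-pain question asks about a kind of pain that section 5.3 excludes, so the listed chronic-pain covariate carries almost no information and the chronic pain that may vary has no item

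*Combined protocol and SAP*

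**What the plan says.** - **Eligibility (section 5.3).** The exclusion reads: "Chronic pain patients; defined as 'persistent or recurrent pain lasting longer than 3 months' [16]. The pain is not due to the gynecological problem". Chronic pain caused by the gynecological problem is therefore not a reason for exclusion.
- **Data collection (Attachment 2, question 13, Yes/No).** "Do you have chronic pain (existing for more than 6 months) not related to the reason of the surgery". No other item on the form asks about chronic pain. Question 17 (indication) is free text completed by the doctor, and question 11 (medication) is free text.
- **Timing (section 9.3).** The questionnaire is completed at T0, on the ward on the day of surgery and before randomisation. Section 9.3 lists chronic pain among the variables it collects.
- **Use (sections 9.1.3 and 11.1).** Section 9.1.3 lists chronic pain as a baseline characteristic that may affect the pain experience. Section 11.1 says of the primary model that "medication use, intoxications, chronic pain, surgical history, indication of surgery, type of planned surgery, will be considered in the statistical analysis", and gives the reason: "These are taken into account because these variables can be possible confounders in the results of the study".

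**The concern.** Sections 5.3 and 11.1 and Attachment 2 each make sense alone but do not fit together. The form asks about pain unrelated to the operation, and a truthful 'Yes' describes a woman whom section 5.3 keeps out. What remains is a column of almost nothing but 'No'. The chronic pain that may legitimately differ between enrolled women, that from the condition being operated on, has no item.

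The plan itself names chronic pain as a characteristic worth taking into account in the analysis of postoperative pain, and section 11.2 intends to compare baseline characteristics between the arms. As the form stands, neither can be done for the kind of chronic pain that matters here. In an open-label trial the gap is hard to fill afterwards, because a pain history taken after randomisation may be given with knowledge of the allocation.

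**Working it through.** **Step 1. Eligibility against question 13.** Take 'the gynecological problem' in section 5.3 to mean the reason for surgery, and cross duration with cause:

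| Duration | Cause | Section 5.3 | Question 13 |
|---|---|---|---|
| 2 months | unrelated | eligible | No |
| 2 months | related | eligible | No |
| 4 months | unrelated | excluded | No |
| 4 months | related | eligible | No |
| 7 months | unrelated | excluded | Yes |
| 7 months | related | eligible | No |

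Every eligible row gives 'No', and the only 'Yes' is in an excluded row. The 4-month unrelated row also shows that question 13 is not a full eligibility check: section 5.3 uses 3 months and question 13 uses 6, so unrelated pain of between 3 and 6 months is excluded but answers 'No'.

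**Step 2. What the model can do with it.** For 60 women, a design matrix with an intercept, treatment group and a constant chronic-pain column has 3 columns but rank 2. The chronic-pain coefficient cannot be estimated, and the term adjusts for nothing.

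**Step 3. What a usable variable could be worth.** The documents give no figure for this, so there is none to reproduce.

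Inputs from section 5.4: SD 20 mm and 30 women per arm. Assumptions, not in the documents: a share p of enrolled women have chronic pain from the condition being operated on, it raises postoperative pain by d mm, and the total SD stays at 20 mm. The calculation treats the outcome as a simple comparison of two means, which simplifies the planned mixed model.

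- Unadjusted SE of the arm difference = 20 × √(2/30) = 5.16 mm.
- Share of variance explained, R² = p(1 − p)d²/20².
- Adjusted SE = 5.16 × √(1 − R²).

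| p | d (mm) | R² | Adjusted SE (mm) | Reduction |
|---|---|---|---|---|
| 0.2 | 10 | 0.16 × 100/400 = 4% | 5.06 | 2% |
| 0.3 | 15 | 0.21 × 225/400 = 12% | 4.85 | 6% |
| 0.5 | 20 | 0.25 × 400/400 = 25% | 4.47 | 13% |

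**Step 4. Chance imbalance, for scale.** With 30 per arm, the 95% range of the shift from imbalance in this variable is 1.96 × d × √(2p(1 − p)/30), which gives 2.0, 3.5 and 5.1 mm for the three rows. The 95% half-width of the unadjusted arm difference is 1.96 × 5.16 = 10.1 mm. The total SD of 20 mm already contains this variable's contribution, so these shifts are part of the 10.1 mm and not an addition to it.

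**The case against.** The case for leaving the plan alone has real weight.

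- **No bias.** A reader might infer that an unrecorded confounder distorts the treatment effect. Section 9.2 describes 1:1 randomisation, so an unmeasured baseline variable does not bias the comparison, and chance imbalance is already in the standard error (step 4). This part of the objection stands in full.
- **Proxies exist.** A reader might infer that none of the lost information is recovered and that any imbalance would go unseen. The documents do not support that. Pain is scored in both arms at T1a, before any VR, and medication use, indication and type of surgery are separate covariates. Each may carry part of the information. None gives the presence and duration of pain from the operated condition, however. The T1a score is a momentary intensity, follows the paracetamol given on arrival, comes after randomisation and is not in the covariate list of section 11.1. Section 13.1 allows data to be taken from the patient file, but expects the patient to supply the information and plans no extraction of pain history.
- **Not strictly constant.** A woman with chronic pain from a second gynecological condition could be eligible and answer 'Yes'. So could a woman enrolled in error: counselling takes place at the outpatient clinic, question 13 is answered on the day of surgery, and no section says that a 'Yes' stops randomisation. This is right, but a few such answers would not represent the pain that matters.
- **No firm commitment.** Section 11.1 says only that the 13 variables will be considered, so losing one does not invalidate the primary model. This also stands, and it limits the severity.
- **Assumed size.** The largest figure needs half the women affected and an effect of 20 mm, more than the 15 mm expected of VR in section 5.4. Nothing in the documents supports that corner, and it should be read only as an upper illustration.

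**Conclusion.** The point holds as a minor design gap. The plan names a covariate that its own eligibility rule makes almost constant, and the related characteristic that can vary among enrolled women is not recorded as a variable. This rests on reading section 5.3's gynecological problem as the reason for surgery, which is the natural reading, and on enrolment following section 5.3.

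The consequence is lost precision and a baseline comparison that cannot be made, not a biased treatment effect. Under the assumed inputs the possible gain in standard error is about 2% to 6% in the two milder scenarios and 13% in the most favourable one. It would be smaller to the extent that the proxies already carry the same information. The primary analysis remains valid without the change.

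**What to change.** 1. Keep question 13 as an eligibility check only, and reconcile its duration threshold with section 5.3 so that the two passages describe the same women.
2. Add one yes/no item to Attachment 2, completed at T0 before randomisation: whether the woman has had pain from the condition for which she is being operated on for longer than 3 months, the duration used in section 5.3's definition (or the single threshold that results from the reconciliation).
3. In sections 9.1.3, 9.3 and 11.1, name this new item in place of the general term chronic pain, and include it in the baseline comparison of section 11.2.

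The cost is one extra form item and wording changes in those sections. No patients, visits or procedures are added. The item should be in place before recruitment. For women already randomised it could be collected only afterwards, possibly with knowledge of the allocation, and should then be treated as missing rather than filled in from recall.

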Attachment 3. State Trait Anxiety Inventory (STA)

A number of statements which people have used to describe themselves are given below. Read each statement and then circle the most appropriate number to indicate how you feel right now, at this moment. There are no right or wrong answers. Do not spend too much time on any statement but give the answer which seems to describe your present feelings best.

1. I feel calm

- Not at all
- Somewhat
- Moderately
- Very much

2. I am tense

- Not at all
- Somewhat
- Moderately
- Very much

3. I feel upset

- Not at all
- Somewhat
- Moderately
- Very much

4. I am relaxed

- Not at all
- Somewhat
- Moderately
- Very much

5. I feel confident

- Not at all
- Somewhat
- Moderately
- Very much

6. I am worried

- Not at all
- Somewhat
- Moderately
- Very much

Attachment 4. Pain catastrophizing scale (PCS)

Pain can give you certain thoughts and feelings. With this questionnaire, we want to measure what you experience when having pain. Down below are 13 allegations about different thoughts and feelings that may have a connection with pain. Try to fill in, in which way these thoughts and feelings are applicable for you. Use the following ranking:

0 = Not at all

1 = Slightly

2 = to a certain extent

3 = largely

4 = always

Circle the number that is most applicable

When I am in pain.....

1. I constantly wonder whether the pain will stop.	0	1	2	3	4
2. I feel I cannot continue like this	0	1	2	3	4
3. It is horrible, and I think it will never get any better.	0	1	2	3	4
4. it is awful and I feel the pain is overwhelming me.	0	1	2	3	4
5. I feel I cannot longer hold on.	0	1	2	3	4
6. I am afraid the pain will get worse.	0	1	2	3	4
7. I keep thinking about other painful events.	0	1	2	3	4
8. I desire that the pain will stop.	0	1	2	3	4
9. I cannot get the pain out of my mind	0	1	2	3	4
10. I keep thinking how much it hurts.	0	1	2	3	4
11. I keep thinking how much I would like the pain to stop.	0	1	2	3	4
12. there is nothing I can do to reduce the intensity of the pain.	0	1	2	3	4
13. I wonder whether something bad can happen.	0	1	2	3	4

Attachment 5. VR-questionnaire

We would like to ask you some questions about your experience with Virtual Reality (VR).

1. How did you experience the use of VR before surgery?

- Very pleasant
- Pleasant
- Neutral
- Unpleasant
- Very unpleasant

2. How did you experience the use of VR after your surgery?

- Very pleasant
- Pleasant
- Neutral
- Unpleasant
- Very unpleasant

3. Did the VR-experience contribute in reducing your pain experience before your surgery?

- Very likely
- Likely
- Pretty likely
- Not likely
- Not likely at all

4. Did the VR-experience contribute in reducing your pain experience after your surgery?

- Very likely
- Likely
- Pretty likely
- Not likely
- Not likely at all

5. Did the VR-experience reduce your anxiety level before surgery?

- Very likely
- Likely
- Pretty likely
- Not likely
- Not likely at all

6. Did the VR-experience reduce your anxiety level after the surgery?

- Very likely
- Likely
- Pretty likely
- Not likely
- Not likely at all

7. Would you choose the use of VR during a surgery under spinal anesthesia the next time you will have to get surgery?

- Very likely
- Likely
- Pretty likely
- Not likely
- Not likely at all

8. The use of the VR-app is easy:

- Completely agree

- Agree
- Neutral
- Disagree
- Completely disagree

9. Would you recommend the use of VR during a surgery under spinal anesthesia to your friends, family or others?

- Very likely
- Likely
- Pretty likely
- Not likely
- Not likely at all

10. How easy was the use of VR before or after surgery?

- Very easy
- Easy
- Pretty easy
- Not that easy
- Not easy at all

11. How visually attractive was the VR-experience before and after surgery

- Very attractive
- Attractive
- Pretty attractive
- Not that attractive
- Not attractive at all

12. Did you prefer anything else in the VR-app?

- No
- Yes, if yes circle what you prefer,

A more active game component
A less active game component
Only relaxing images

13. Did you experience any side-effects during the use of the VR-app?

- No
- Yes, if yes circle the side-effects;

Nausea
Dizziness
Other:

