9.1.2 Secondary study parameters

Secondary outcomes will be:

- Pre-operative anxiety (State-Trait Anxiety Inventory (STAI)-6 questionnaire)
- Pain catastrophizing (Pain Catastrophizing Scale questionnaire)
- Difference in anxiety scores pre- and post VR intervention (NRS)
- Analgesic use (daily use of paracetamol, NSAIDs, opioids)
- Length of hospital stay
- Tolerability, feasibility and satisfaction of VR use (questionnaire)
- Preoperative pain score (NRS)

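### VR-questionnaire items 3–6 have no answer for women without pain or anxiety, so they cannot separate 'no symptom to reduce' from 'VR did not help'

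*Combined protocol and SAP*

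**What the plan says.** Section 9.1.2 lists the questionnaire as a secondary outcome: "Tolerability, feasibility and satisfaction of VR use (questionnaire". Section 9.3 has it completed on the ward after surgery.

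Four of its items ask about perceived effect on symptoms:

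- Item 3, pain before surgery: "Did the VR-experience contribute in reducing your pain experience before your surgery"
- Item 4, pain after surgery: "Did the VR-experience contribute in reducing your pain experience after your surgery"
- Item 5, anxiety before surgery: "Did the VR-experience reduce your anxiety level before surgery"
- Item 6, anxiety after surgery: "Did the VR-experience reduce your anxiety level after the surgery"

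Each has the same five options, the lowest being "Not likely at all". None has a not-applicable answer, a filter question, a skip instruction or a neutral midpoint, although items 1, 2 and 8 of the same form do offer a neutral answer.

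The planned analysis is one sentence in Section 11.2: "The tolerability, feasibility and satisfaction of VR use will be calculated into means and frequencies". It gives no item scores, does not define a favourable answer and does not restrict the items to women who had the symptom. The general rule in Section 11 is that missing values are excluded or imputed depending on how many there are; no threshold is given.

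Separately, Sections 6.1 and 9.3 record NRS pain and anxiety at T1a (before preoperative VR), T2 (arrival at recovery, before postoperative VR) and T3 (before leaving recovery). The plan does not link these scores to items 3–6.

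**The concern.** Each item presupposes that there was something to reduce. A woman with no pain before surgery who answers item 3 literally may tick the lowest option. That answer enters the summary exactly like one from a woman who was in pain and found VR useless. The two mean different things, and the planned summary cannot tell them apart.

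Such women are foreseeable, at least for item 3. Surgery is elective, paracetamol is given on arrival under the standard pain protocol (Section 6.1), and Section 5.3 excludes "Chronic pain patients; defined as 'persistent or recurrent pain lasting longer than 3 months", with the qualifier that the pain is not due to the gynecological problem.

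At stake is the meaning of the only items on the form that ask patients whether VR helped their pain or anxiety. Their results would depend partly on how many women had symptoms and partly on how symptom-free women chose to answer.

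**Working it through.** The documents give no figure for these items, so there is nothing to reproduce. The check sets the item format against the analysis text and then illustrates the possible size.

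**Text check.** An answer from a symptom-free woman can reach the summary in three ways.

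1. She ticks an unfavourable option. It is counted with the answers of women whom VR did not help.
2. She leaves the item blank. Under Section 11 the blank is excluded, which does no harm, or imputed, which gives her a benefit rating for a symptom she did not have.
3. She ticks a favourable option, for instance because VR was pleasant. It is counted with the answers of women whom VR did help.

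Nothing in Attachment 5 or Section 11.2 determines which of these happens.

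**Illustration.** Inputs:

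- n = 30 women in the VR group (Section 5.4).
- q = share who are symptom-free in the period asked about. Assumed; shown from 10% to 70%.
- f = 60%, the favourable share among women with the symptom. Assumed. 'Favourable' itself is also an assumption, because the plan does not define it.

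Formulas for the reported favourable share:

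- all symptom-free women answer unfavourably: (1 − q) × f
- all skip and are excluded: f
- all answer favourably: (1 − q) × f + q

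At q = 30%: 0.70 × 0.60 = 42%; 60%; and 0.42 + 0.30 = 72%.

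| q | women with the symptom, of 30 | all unfavourable | skipped and excluded | all favourable |
|---|---|---|---|---|
| 10% | 27 | 54% | 60% | 64% |
| 20% | 24 | 48% | 60% | 68% |
| 30% | 21 | 42% | 60% | 72% |
| 50% | 15 | 30% | 60% | 80% |
| 70% | 9 | 18% | 60% | 88% |

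The gap between the two extremes always equals q. Means behave in the same way. On an assumed 1–5 score with mean 4 among women with the symptom, q = 30% gives 0.7 × 4 + 0.3 × 1 = 3.1 at one extreme and 0.7 × 4 + 0.3 × 5 = 4.3 at the other.

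Nor can a reported share be read backwards. A result of 42% fits q = 30% with f = 60% and all symptom-free women answering unfavourably. It fits equally well with q = 0 and f = 42%.

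**After the fix.** If symptom-free women are identified and left out, the share is f for any q. The denominator falls to the number in the second column.

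**The case against.** A reader might infer that women without symptoms are forced into answers that count as VR failures. The documents do not support that. No text makes an answer compulsory, no failure or responder category is defined, blanks may be excluded, and a symptom-free woman may tick a favourable box. A downward bias is plausible but not established; the 42% above is one extreme, not a central estimate.

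Three further objections have weight.

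- **The number affected is unknown.** The exclusion in Section 5.3 leaves room for women whose chronic pain comes from the gynecological condition, and no document gives the share without pain. For item 5, nothing suggests that many women would be free of anxiety before surgery.
- **The outcome is modest.** The named outcome is tolerability, feasibility and satisfaction. Effects on pain and anxiety are assessed by NRS between groups with linear mixed models (Sections 11.1 and 11.2), which these items do not touch. A reader might also infer that a comparison of preoperative with postoperative ratings is spoiled, but no such comparison of questionnaire items is planned.
- **The NRS scores already allow a partial repair.** This is true before surgery but less so afterwards. T2 is scored on arrival at recovery after spinal anesthesia, while items 4 and 6 cover the whole period after surgery, and a second VR session can follow in a stay of more than 3 hours. A woman scoring 0 at T2 may have pain later, so filtering on T2 alone would drop women to whom the item applies.

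These points limit the size and scope of the concern. They do not remove it: with neither an answer option nor an analysis rule, the ambiguity remains whichever way symptom-free women answer.

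**Conclusion.** The point holds as a limit on interpretation. As designed and analysed, items 3–6 cannot distinguish a woman with nothing to reduce from one whom VR did not help, so their means and frequencies cannot be read as perceived benefit. With 30% symptom-free and 60% favourable among the rest, the reported share could lie anywhere from 42% to 72%. Both inputs are assumptions, and how symptom-free women would answer is unknown.

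The importance is minor: a few items within one descriptive secondary outcome that concerns VR users only. The primary comparison and the sample size are unaffected.

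**What to change.** - **Form.** Add 'I had no pain at that time' to items 3 and 4, and 'I was not anxious at that time' to items 5 and 6.
- **Analysis (Section 11.2).** Report each of these items among women who did not tick the new box. Show the denominator and the number who ticked it. State that blanks on these four items will not be imputed.
- **Supporting analysis, or the fallback if forms are already in use.** Report items 3 and 5 among women with the matching NRS (pain or anxiety) above 0 at T1a, and items 4 and 6 among those with it above 0 at T2 or T3. State that symptoms arising and resolving between measurements can be missed, and that T3 is scored after VR.

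The cost is four tick boxes and a few lines of analysis text; the supporting analysis needs no new data. The downside is smaller denominators, for example 21 instead of 30 if 30% are symptom-free, which show how many answers are informative.
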